1.0 Research Design

1.1 Purpose/Specific Aims

The purpose of the proposed study is to compare the effectiveness of video instructions versus a patient handout as method for patient comprehension and opioid usage for meniscectomy patients.

A. Objectives

The primary objective is to compare the effectiveness of video instructions versus a patient handout as method for patient comprehension of concept areas such as how to care for the incision, how to safely manage pain with and without opioids, the side effects of opioids. The secondary objective is to evaluate whether the utilization of video instructions versus a patient handout will lead to lower post-operative use of opioid medications.

B. Hypotheses / Research Question(s)

The use of video for pre-operative education for meniscectomy surgery will improve patient comprehension of operative instructions compared to paper handout. Secondly, the use of video will help to minimize opioid usage post-operatively.

1.2 Research Significance

Several studies have shown the utility of video relating to patient comprehension and experience surrounding orthopedic surgery. These studies have been done in knee and shoulder arthroscopy, joint replacement surgery, and hand surgery. A recent project referenced below that was presented at NYSSH meeting showed that using video compared to a paper handout for operative instructions showed improved patient comprehension, particularly as it relates to patient knowledge surrounding opioid usage. However, that study did not quantify the number of opioids in the video and paper handout groups. To date, there is no study that compares video instructions versus a paper handout for patient comprehension and opioid usage for meniscectomy patients.

1.3 Research Design and Methods

This is a single-blinded prospective randomized controlled clinical trial. Patients 18 or older, undergoing a meniscectomy procedure at University Center for Ambulatory Surgery, LLC (UOA), who are English speaking, with intact decision-making capacity, and have access to the required technology to participate in this study (cell phone to receive text messages and view the instructional video), will be reviewed for eligibility. Patients who did not speak English and/or had documented cognitive impairment or neurological disorder affecting word processing or memory will be excluded from the study. Once identified, potential study subjects will be asked whether they are interested in participating in the project. If the patient agrees, the subject will be given the informed consent to read and sign.

A. Research Procedures

Preoperative Visit: All patients who consent will have operative instructions explained by the study surgeon and his assistants. Patients will then be allocated to either the video or handout group with the use of a computer-generated block randomization sequence, with the study surgeon blinded to patient allocation. Due to the nature of the material provided, it is not possible to blind the patients to the allocation. Patients in the control group will be given a physical copy of the handout of operative guidelines at the time they book their surgery in the office. Those in the study group will receive a link at the same time point when they book their surgery in the office, via email, which will provide access to a video on YouTube outlining the same operative instructions. A research assistant will confirm patients in the study group receive the video by email and that the link was playable/ accessible to them.

Patients in both groups will be aware that they would be asked questions regarding the contents of the instructions. Patients had unlimited access to the video once they were provided the link. The

video was less than 10 minutes long, and it was accessible by computer, tablet, or cell phone. The content of the video and paper handout mirrored each other and consisted of general operative instructions, incision and dressing care, symptom monitoring, and pain management (Video 1, Appendix 1).

Day of Surgery: All patients will be receiving the same preoperative care, undergo meniscectomy via the same surgical technique, and same postoperative care in the post-anesthesia care unit (PACU) after surgery. In the PACU, patients in the control group will again be given a physical copy of the handout of operative guidelines. Likewise, patients in the study group will also be sent a link by email, again in the PACU after surgery.

After surgery: At the first postoperative visit, 10 to 14 days after surgery, patients will be given a questionnaire to evaluate their comprehension of concepts which were outlined in the video or the handout. The questionnaire will consist of 12 multiple choice questions with concepts including areas such as how to care for the incision, how to safely manage pain with and without opioids, the side effects of opioids (Questionnaire in supplemental section of eIRB). Patients will also be asked to rate how helpful they found the information in the assigned instructions on a scale of 1 to 5 (1 = not at all helpful, 5 = extremely helpful), how many times they viewed the instructions, and at what time point the instructions were most helpful to read (before the procedure, at the surgical center, or after the procedure). Lastly, patients will be asked to report the number of opioid and other analgesic medications they took following surgery.

B. Data Points

Age, injury type, surgery performed, use of narcotic and other analgesic pain medication, number of times instructions viewed or read

C. Study Duration

The study will be conducted from time of IRB approval until the minimum number of participants shown below have completed the study. Each subject will participate in the study from their pre-operative appointment until 14 days after surgery.

D. Endpoints

Primary endpoints: The number of questions answered correctly, and patient-reported helpfulness of the material, on a scale of 1-5 to detect clinically significant difference in patient comprehension.

Secondary endpoint: Number of opioid and other analgesic medications taken

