1.9 Data Collection

A. Primary Data Collection

B.

- **Location**: Data will be collected via online survey/questionnaire utilizing RedCAP
- **Process of Data Collection**: Patients will be educated on how to access the online survey and a research assistant will ensure patient access.
- **Timing and Frequency**: The survey will be accessible to patients at their first post-operative visit, day 10-14.
- **Procedures for Audio/Visual Recording**: *N/a*
- **Study Instruments**: Qualitative data will be collected via a questionnaire created by the researchers.
- **Ethnographic Studies, Interviews, Or Observation**: Patients will be provided with questionnaires via the app/web based system including pain scores, number of narcotic and non-narcotic pain medications used, as well as any adverse events.
- **Subject Identifiers**: Patient data will not include any identifiers.

C. Secondary Data Collection

Not Applicable

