4.3 Number of Subjects

A. Total Number of Subjects

80-160 patients targeted to be recruited to account for study dropout

B. Total Number of Subjects If Multicenter Study

N/a

C. Feasibility

University Orthopaedic Associates is a high-volume orthopaedic center. Physicians including Drs. [name], [name], [name], and [name] see a high volume of patients undergoing meniscectomy and it is therefore reasonable to accrue the required number of patients to achieve statistical significance for this study.

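### The opioid endpoint is a self-reported count, and no strength or quantity supplied is listed for collection, so it lacks a common unit if discharge prescriptions differ

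*Protocol*

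**What the plan says.** Protocol section 1.3 A (Day of Surgery) states that all patients have the same preoperative care, the same surgical technique and the "same postoperative care in the post-anesthesia care unit (PACU) after surgery". No section shown describes analgesia prescribed at discharge.

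Opioid use is then measured over the period after discharge. At the first postoperative visit "patients will be asked to report the number of opioid and other analgesic medications they took following surgery". Section 1.3 D defines it as "Secondary endpoint: Number of opioid and other analgesic medications taken", and section 1.9 again asks for the "number of narcotic and non-narcotic pain medications used, as well as any adverse events". The data points in 1.3 B are "Age, injury type, surgery performed, use of narcotic and other analgesic pain medication, number of times instructions viewed or read".

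On who treats the patients, section 4.3 C names four physicians, as examples, who "see a high volume of patients undergoing meniscectomy", whereas section 1.3 A speaks of a single study surgeon. Allocation uses a "computer-generated block randomization sequence, with the study surgeon blinded to patient allocation"; stratification by surgeon is not mentioned. Section 6.1 gives unadjusted two-group tests for secondary variables.

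**The concern.** Lower opioid use is the secondary hypothesis (1.1 B), and section 1.2 justifies the trial partly because an earlier comparison of video and handout did not quantify opioids. The measure therefore has to carry meaning as an amount of opioid.

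A bare count does so only if the units are alike. A patient whose units are twice as strong can take the same total and report half the number. Without a refill, a patient cannot report more than was supplied. As the data points are written, neither case could be recognised, and the self-report has no supplied quantity to be checked against. The endpoint wording also joins opioids and other analgesics, which have no common unit as a count.

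This belongs in the protocol. An analysis plan can define a conversion, but it cannot convert data that were not collected. Later recovery is doubtful: section 1.9 says patient data will carry no identifiers, and section 7.0 says data are deleted at completion.

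**Working it through.** **The plan's own figures.** The protocol gives no figure for the opioid endpoint. Its only power figures are in section 1.5, and they reproduce. A two-sided two-sample t-test at alpha 0.05 and power 0.80 (sidedness is not stated and is assumed) gives 64, 45, 34 and 26 per arm for effect sizes 0.50, 0.60, 0.70 and 0.80. Dividing by 0.8 for 20% dropout and rounding up gives 80, 57, 43 and 33. Section 4.3 A targets 80 to 160 in total, that is 40 to 80 per arm before dropout.

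**Illustration 1: strength varies and intake follows total amount.** The inputs are assumptions; the documents give none. Half the patients have units of relative strength 1 and half of relative strength 2, independent of the total amount D. The count is D/s.

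- E[1/s] = 0.5 × 1 + 0.5 × 0.5 = 0.75
- E[1/s²] = 0.5 × 1 + 0.5 × 0.25 = 0.625
- E[1/s²] / E[1/s]² = 0.625 / 0.5625 = 1.111
- CV²(count) = (1 + CV²(D)) × 1.111 − 1

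| CV of D | CV² of count | Ratio to CV² of D | Equivalent loss of patients, 1 − 1/ratio |
|---|---|---|---|
| 0.7 | 0.656 | 1.34 | 25% |
| 1.0 | 1.222 | 1.22 | 18% |
| 1.5 | 2.611 | 1.16 | 14% |

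With identical strengths the factor 1.111 becomes 1 and the loss is nil.

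**Chance imbalance in the same model.** Suppose 45% of one arm and 55% of the other have the stronger unit. Mean 1/s is 0.55 + 0.45 × 0.5 = 0.775 against 0.45 + 0.55 × 0.5 = 0.725. The difference is 0.05 / 0.75 = 6.7% of the mean count. The count's CV is 0.81, 1.11 or 1.62 (square roots of the second column), so this is about 0.08, 0.06 or 0.04 SD. The standard error of an arm difference with 40 per arm is √(2/40) = 0.22 SD. An imbalance of this size sits well inside ordinary sampling error, which already includes it.

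**Illustration 2: prescribers differ in general.** This was simulated with four surgeons, unstratified 1:1 allocation and an unadjusted t-test, 5,000 runs per setting. The share of total variance due to prescriber is assumed to be 0.1, 0.3 or 0.5. The true effect is 0.8 (26 per arm) or 0.5 (64 per arm) within-prescriber SDs.

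| Prescriber share | Power (0.80 without prescriber variance) | SD of prescriber part of arm difference, 26 / 64 per arm |
|---|---|---|
| 0.1 | 0.77 | 0.08 / 0.05 |
| 0.3 | 0.69–0.70 | 0.16 / 0.10 |
| 0.5 | 0.59–0.60 | 0.24 / 0.15 |

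The prescriber part of the arm difference averaged below 0.004 SD in absolute value, and type I error stayed between 0.046 and 0.056. The result is lost power without bias.

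**The case against.** A reader might infer that prescriber differences are confounded with the effect of the video. The documents do not support that. Patients are individually randomised and the study surgeon is blinded to allocation, so prescribing habits do not differ by arm in expectation, and the simulation agrees. Nor is chance imbalance a second harm on top of noise; the standard error already covers it. This objection stands in full.

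A reader might also infer that strength and supply will not be recorded at all. That cannot be known. The questionnaire is held in the eIRB and is not shown, and the data point on use of narcotic and other analgesic medication is broad enough to include drug and strength. One can say only that these items are not stated to be collected.

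The number of prescribers is not settled either: 4.3 C is a feasibility statement and 1.3 A refers to one study surgeon. No section says that strengths vary.

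The illustration depends on behaviour too. If patients take units by number whatever the strength, strength adds no noise to the count, and converting to amount adds it instead. In the same 50/50 model, E[s²] / E[s]² = 2.5 / 2.25 = 1.111, the same factor. This is a good reason to report both measures. It does not rescue the count as a measure of how much opioid was used.

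Finally, conversion rules and covariates are commonly left to an analysis plan. That is fair for the analysis, but not for the data fields on which it depends.

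**Conclusion.** The point holds as one of measurement on the secondary endpoint. As the protocol is written, opioid use is a self-reported number with no stated unit, strength or supply, and sameness of care is stated only through the PACU. If discharge prescriptions differ, the count is a noisier and less interpretable measure of opioid use.

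The size is uncertain because the documents give no prescribing data. Under the first set of assumptions the relative variance rises by 16% to 34%. Under the second, power falls from 0.80 to between 0.77 and 0.59. If prescribing is identical, these losses are nil. The comprehension and helpfulness comparisons are untouched, and no systematic difference between arms is expected. The change is still worth making, because it is cheap and the information may not be recoverable later.

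**What to change.** - Add to 1.3 B the discharge opioid's name, strength per unit, initial quantity supplied, any refill, and prescriber, captured under the study code. Section 1.9 marks secondary data collection as not applicable and says patient data carry no identifiers, so that text must be reconciled with chart abstraction.
- Ask patients for the number remaining as well as the number taken.
- Analyse opioids separately from other analgesics, as number taken × recorded strength on a common equivalence scale, and report the raw count alongside.
- If the comparison is adjusted, use only the initial quantity supplied or the prescriber. Refills follow randomisation and may be affected by the video, so record them but do not adjust for them.
- Reconcile the single study surgeon in 1.3 A with the physicians named in 4.3 C. If discharge prescribing is in fact uniform, one sentence saying so would settle most of the point.

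No change to what anyone prescribes is proposed. The cost is a few fields per patient, one survey item and a little abstraction time.

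### Analgesic use is self-reported by unblinded patients after a test on opioid safety; asking it first would remove one avoidable route to reporting bias

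*Protocol*

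**What the plan says.** The secondary endpoint in Protocol 1.3 D is the number of opioid and other analgesic medications taken. Section 1.3 A gives its source and place in the sequence. The visit is described as "At the first postoperative visit, 10 to 14 days after surgery, patients will be given a questionnaire to evaluate their comprehension of concepts". The test has 12 multiple-choice items, and its listed topics include safe pain control with and without opioids and opioid side effects. Ratings of the material follow, and then: "Lastly, patients will be asked to report the number of opioid and other analgesic medications they took following surgery".

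Section 1.9 gives one time point: "The survey will be accessible to patients at their first post-operative visit, day 10-14". It also says "Patients will be provided with questionnaires via the app/web based system including pain scores, number of narcotic and non-narcotic pain medications used", which is again completed by the patient and has no timing of its own. The entry under "C. Secondary Data Collection" is not applicable.

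On blinding, 1.3 A says "Due to the nature of the material provided, it is not possible to blind the patients to the allocation"; only the study surgeon is blinded. Section 1.1 B states the expected direction: "Secondly, the use of video will help to minimize opioid usage post-operatively". Section 1.2 names opioid quantity as the gap left by the earlier handout-versus-video study: "However, that study did not quantify the number of opioids in the video and paper handout groups".

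**The concern.** The person who measures this outcome is the patient, who knows the allocation. Blinding the surgeon does not protect it, because the surgeon does not record it. In the order that 1.3 A gives, patients work through questions on opioid safety and side effects just before they say how many tablets they took over the preceding 10 to 14 days. A patient who has taken that content in well may shade the count downwards.

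If the video teaches the opioid content better, as the trial hopes, such shading would be greater in the video arm and would look like the reduction in use set out in 1.1 B. At stake is the reading of the opioid result, which 1.2 presents as what this trial adds. The comprehension score is not affected.

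**Working it through.** **Step 1: the facts, set side by side**

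- Source: patient report only (1.3 A, 1.9). No other source is named.
- Timing: the day 10-14 visit is the only one stated (1.3 A, 1.9).
- Order: 12-item test, ratings, then the medication count (1.3 A). The form itself is in the eIRB supplement and not shown, so the order is read from the narrative.
- Blinding: patients unblinded (1.3 A).
- Content: video and handout mirror each other, and both arms take the same test (1.3 A).

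**Step 2: what a between-arm bias requires**

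The prompt from the test is common to both arms and on its own shifts both equally. A spurious difference needs two links:

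1. The arms differ in how well they have absorbed the opioid content. The protocol hypothesises better comprehension with video (1.1 B). Section 1.2 adds that the earlier study found this particularly for knowledge about opioids.
2. That learning lowers reported counts beyond any fall in actual use. The protocol has nothing for or against this.

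**Step 3: the plan's sample size, for scale**

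A two-sample t-test at two-sided alpha 0.05 and power 0.80 gives 64, 45, 34 and 26 per arm for effect sizes 0.50, 0.60, 0.70 and 0.80. Dividing by 0.8 for drop-out gives 80, 57, 43 and 33. Both rows match the table in 1.5. The illustration uses 64 per arm.

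**Step 4: illustration under assumed inputs**

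The protocol gives no mean, SD or reporting error for opioid use. Assumed: gamma-distributed counts with mean 8 and SD 8 in both arms, no true difference, and video-arm reports multiplied by (1 − u), where u is the extra under-reporting.

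- Spurious difference = 8u, so 0.8, 1.6 and 2.4 tablets for u = 0.10, 0.20 and 0.30.
- Pooled SD = √[(8² + (8(1 − u))²)/2] = 7.61, 7.24 and 6.90.
- Standardised shift = 8u / pooled SD = 0.105, 0.221 and 0.348.
- Expected z = shift × √(64/2) = 0.59, 1.25 and 1.97.
- P(reject) = P(Z > 1.96 − z) + P(Z < −1.96 − z) = 9.1%, 23.9% and 50.2%.

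Simulation agrees. Section 6.1 also allows the Mann-Whitney test for continuous secondary variables, so both tests are shown, with counts rounded to whole tablets for Mann-Whitney:

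| Extra under-reporting | t-test, 64 per arm | Mann-Whitney, 64 per arm |
|---|---|---|
| none | about 5% | about 5% |
| 10% | about 9% | 8% to 9% |
| 20% | 23% to 24% | about 19% |
| 30% | about 50% | 40% to 41% |

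Section 4.3 targets 80 to 160 patients in total. At 20% under-reporting the t-test rate is about 16% with 40 per arm and 28% with 80 per arm; Mann-Whitney gives about 13% and 23%. A larger trial does not dilute a bias of this kind; it makes a false positive more likely.

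**The case against.** The strongest reply is that both arms receive mirrored content, hear the instructions explained by the surgical team and take the same test, so the prompt is not differential. This stands for the prompt alone. What remains is a differential response to it, and the second link in that chain has no support in the protocol.

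A reader might go further and infer that the materials tell patients to limit opioids. The protocol does not say so. Section 1.3 A describes the content as general instructions, incision and dressing care, symptom monitoring and pain management, and the video and handout are not shown. Lower use is the investigators' aim in 1.1, not a documented message to patients.

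Three further points have weight:

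- The word that places the medication question last may order only the narrative and not the form.
- A single report is the likelier reading of 1.9, but it is not explicit.
- Answers go into an online survey described in 1.9 as carrying no identifiers, which plausibly lowers the pressure to please.

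Finally, the endpoint is secondary, and self-report is a disclosed choice, not an error. That limits the weight of the point but does not count against a change of question order that costs nothing.

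**Conclusion.** The point holds as a plausible, directional threat to the secondary endpoint. The protocol supports these facts: unblinded self-report, one stated time point, a described order that puts opioid-safety questions first, and no objective check.

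It does not support the stronger reading that a lower count in the video arm would be an artefact, or that the test by itself biases the comparison. Bias needs differential learning that also changes reporting, and the second condition is unverified.

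The false-positive rates of about 9%, 24% and 50% (t-test) or 9%, 19% and 40% (Mann-Whitney) rest wholly on the assumed mean, SD, distribution and under-reporting. They show how sensitive the comparison would be and do not estimate what will happen.

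**What to change.** In 1.3 A and 1.9, state that the medication-use items come first in the REDCap form, before the comprehension test and the helpfulness rating. This costs nothing. It removes the prompt from the test but not any under-reporting that comes from the learned content itself.

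Optionally, keep self-report as the endpoint and record the opioid tablets remaining at the visit and the quantity prescribed, as a supporting sensitivity check. The cost is one reminder, one form field and one chart item per patient. This should not replace the endpoint:

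- A count read off by the patient is still self-report.
- Discarded tablets would count as taken.
- Forgotten bottles would leave gaps, or a mixed measure if self-report filled them.
- Other analgesics would still rest on recall.

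The protocol should name missing bottles and discarded tablets as limits of the check. In either case, describe and interpret the result as self-reported use.

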1.5 Sample Size Justification

PG Power Table			Primary 2 Arm Treatment Comparison		Primary 2 Arm Treatment + Anesthesia Subgroup Comparison	
Statistical Significance	Power	Desired Effect Size	N per Treatment Type (2 Groups) 0% Drop-Out Inflation	N per Treatment Type (2 Groups) 20% Drop-Out Inflation	N per Treatment Type (4 Groups) 0% Drop-Out Inflation	N per Treatment Type (4 Groups) 20% Drop-Out Inflation
0.05	0.80	0.50 (medium)	64	80	128	160
0.05	0.80	0.60 (medium)	45	57	90	114
0.05	0.80	0.70 (medium)	34	43	68	86
0.05	0.80	0.80 (large)	26	33	52	66

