4.0 Subject Considerations

4.1 Subject Selection and Enrollment Considerations

A. Method to Identify Potential Subjects

Patients 18 or older, undergoing a meniscectomy procedure at University Center for Ambulatory Surgery, LLC (UOA) will be reviewed for eligibility.

B. Recruitment Details

Recruitment will take place at the UOA office during patient visits. Patients will be provided with educational pamphlet. Recruitment will take place by study staff.

C. Subject Screening

Subjects will be screened by attending physicians in the office setting as patients are being indicated for surgery as per standard of care.

▪ Inclusion Criteria

- Patients 18 or older
- Undergoing a meniscectomy procedure
- English speaking
- Intact decision-making capacity
- Have access to the required technology to participate in this study (cell phone to receive text messages and view the instructional video)

▪ Exclusion Criteria

- Patients who did not speak English
- Patients with documented cognitive impairment or neurological disorder affecting word processing or memory
- Patients who do not have access to a cell phone to view the video

D. Privacy Protections

Data collected via an online questionnaire that is protected by HIPPA regulations. Data will be de-identified prior to statistical analysis.

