6.0 Data Management Plan

6.1 Data Analysis

Data will be analyzed by the statisticians. Statistical comparisons will be made between patients receiving paper instructions vs. video instructions. The mean number of questions answered correctly for both the groups were compared using the student t-test. For secondary variables and baseline characteristics, statistical testing was performed based on the type of variable: the chi-square test for categorical variables and the student t-test (parametric) or Mann-Whitney U test (nonparametric) for continuous variables. For the ordinal variable of patient-reported helpfulness, the Mann-Whitney U test was used.

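### Preoperative opioid use is not among the recorded items, so the opioid comparison gives up some precision and chance imbalance in prior use cannot be seen or adjusted for

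*Protocol*

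**What the plan says.** Protocol section 1.1 sets as secondary objective whether video instruction "will lead to lower post-operative use of opioid medications". Section 1.3 D names the number of opioid and other analgesic medications taken as the secondary endpoint.

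The data points in section 1.3 B are "Age, injury type, surgery performed, use of narcotic and other analgesic pain medication" and the number of times the instructions were viewed. Section 1.3 A has patients report, at the first postoperative visit, what they took after surgery. Section 1.9 opens the only survey at day 10 to 14 and marks secondary data collection as not applicable.

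The exclusions in section 4.1 C are lack of English, lack of a cell phone, and "Patients with documented cognitive impairment or neurological disorder affecting word processing or memory". Opioid use before surgery is not among them. Allocation follows a "computer-generated block randomization sequence" (section 1.3 A), with no stratification mentioned.

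Section 6.1 states that for secondary variables and baseline characteristics "statistical testing was performed based on the type of variable". For continuous variables that means a t-test or a Mann-Whitney U test. No covariate is named.

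**The concern.** Opioid use before surgery is a plausible strong predictor of opioid use after it. Where such patients are eligible, a baseline record does two jobs: it shows whether the arms happened to differ, and it removes explained variance from the comparison.

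This cannot simply be left to an analysis plan. A plan may add a covariate later, but only one that was collected. Recovery afterwards is doubtful: section 1.9 says the data carry no identifiers, and section 7.0 says they are deleted at completion. Asking about prior use at day 10 to 14 would give recall obtained after randomisation.

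At stake is the precision and readability of the only secondary objective. The primary comparison is not affected.

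**Working it through.** **The plan's own figures.** The table in section 1.5 uses significance level 0.05, power 0.80 and standardised effects of 0.50, 0.60, 0.70 and 0.80. A two-sided two-sample t-test gives 64, 45, 34 and 26 per arm. Dividing by 0.8 for the "20% Drop-Out Inflation" gives 80, 57, 43 and 33. Both rows agree with the table. It sizes the primary comparison; nothing is given for the opioid count.

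**Arm sizes.** Section 4.3 targets 80 to 160 patients. At 1:1 (assumed; the ratio is not stated) that is 40 to 80 per arm, and after 20% dropout 32 to 64 per arm.

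**Assumed inputs.** Section 1.4 reports no preliminary data, so the following are assumptions: non-users take a mean of 10 tablets (SD 8); prior users have r = 2 to 3 times that mean and SD; a share f = 5% to 20% are prior users.

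**Variance explained by prior use.**

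Within = (1 − f) × 8² + f × (8r)²; between = f(1 − f) × (10r − 10)²; R² = between / (within + between). The standard error falls by the fraction 1 − √(1 − R²), and the equivalent gain in patients is 1/(1 − R²).

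| f | r | Within | Between | R² | SE reduction | Gain in N |
|---|---|---|---|---|---|---|
| 0.05 | 2 | 73.6 | 4.75 | 0.061 | 3% | 1.06 |
| 0.10 | 3 | 115.2 | 36 | 0.238 | 13% | 1.31 |
| 0.20 | 3 | 166.4 | 64 | 0.278 | 15% | 1.38 |

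**The middle row in tablets, 32 per arm.** Unadjusted SE = √(2 × 151.2/32) = 3.07. Adjusted SE = √(2 × 115.2/32) = 2.68. The part due to chance imbalance in prior users has SD √(2 × 0.10 × 0.90/32) × 20 = 1.50 tablets (1.06 at 64 per arm). It is a component of the 3.07, not an addition to it: 2.68² + 1.50² ≈ 3.07².

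**Power, including the rank test.** A simulation of overdispersed counts (2000 trials per setting) used 64 per arm, a non-user mean of 8, a 35% reduction, and prior users at four times the non-user mean. That multiplier lies beyond the range above.

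| Prior users | t-test | ANCOVA | Mann-Whitney | Rank-ANCOVA |
|---|---|---|---|---|
| 5% | 0.58 | 0.66 | 0.63 | 0.65 |
| 10% | 0.49 | 0.64 | 0.60 | 0.66 |

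Adjustment is worth about 9 to 15 points against the t-test, but only about 2 to 6 against Mann-Whitney. Type I error stayed between about 0.04 and 0.06 for all four methods.

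**The case against.** A reader might infer that a few prior users could dominate the opioid result or decide its direction. The documents do not support that. Even under the assumptions above, 72% to 94% of the variance is unrelated to prior-use status. The ordinary standard error already includes chance imbalance, and type I error is intact. Nor is the comparison biased, since prior use precedes randomisation.

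Section 6.1 also allows Mann-Whitney, a likely choice for a skewed tablet count, and ranks limit the pull of heavy users. That stands, and it shrinks the gain.

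The list in section 1.3 B is not exhaustive: it omits the comprehension and helpfulness scores, and the pain scores and adverse events of section 1.9. Its medication item carries no time qualifier, and the questionnaire sits in a supplement that is not shown. A preoperative item is therefore not strictly ruled out. The postoperative reading is still the natural one, because the procedure text limits the question to use after surgery and the only survey comes at day 10 to 14.

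Finally, the choice of covariates is commonly left to an analysis plan. That is fair for the model term, but not for collecting the variable.

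**Conclusion.** The point holds as a low-severity one about precision and visibility on the secondary endpoint. Prior opioid users are eligible, no preoperative opioid item is named, and the stated tests are unadjusted. The comparison is valid but less precise than it could be, and nobody could check afterwards whether the arms differed in prior use.

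The loss is about 3% to 15% of the standard error on the mean scale, and less with Mann-Whitney. It rests wholly on assumed prevalence and tablet counts. If prior use is rare and its excess modest, the gain sits at the bottom of that range.

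**What to change.** Add to section 1.3 B an item such as: opioid use before surgery (yes/no, recorded at booking before randomisation). Align section 1.9, which at present describes only the postoperative survey. Report the item by arm, and pre-specify it as a covariate in the opioid-count analysis, by regression with robust errors or rank-ANCOVA.

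This is preferable to a stratified van Elteren test, because the prior-user stratum may be empty in one arm. At 5% prevalence and 32 per arm, the chance that at least one arm has no prior user is 1 − (1 − 0.95³²)² ≈ 0.35. A regression with a yes/no term draws no information on the arm difference from those patients in that case either, but it runs as specified without dropping a stratum.

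The cost is one data item and one model term, with little return if prior use is rare. A yes/no item also ignores the amount of prior use. Eligibility and clinical care are unchanged.
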